buffer, and 4 received buffer alone. This design was repeated for the 5 log and 6 log CFU doses, except that 4 additional subjects were given buffer alone. Symptoms and fecal excretion of SC602 were monitored among vaccinees and their household contacts for up to 56 days. Diarrhea was not reported at any of the vaccine dose levels. Minor symptoms were commonly reported among most study participants, but there was no difference between vaccinees and controls and no dose-relationship. In the 6 log CFU dose group, 1 vaccinee had low grade fever, and 2 reported body aches. No increase in symptoms was seen among household contacts. SC602 was not isolated from any vaccinee, household contact or diarrhea case occurring in the neighborhood. The adult trials suggest minimal vaccine shedding, minimal reactogenicity, no transmission risk, and little immune stimulation in this *Shigella*-exposed population.

Inpatient trial: schoolchildren

Nine subjects age 5-15 years old were randomized 3 each to receive 10^4 , 10^5 or 10^6 CFU. No severe symptoms, fever or diarrhea followed vaccination, though 1-2 loose stools occurred in 4 of 9, and abdominal pain in 2 of 9. All symptoms were mild, except 1 report of moderate abdominal cramps in a 6 log CFU recipient.

Overall, symptoms were not serious and not dose related. One subject passed a few drops of blood of unclear origin on day 5 with normal stool and did not excrete SC602. Stool microscopy revealed <10 WBC's per HPF, hookworms and other worms. Rectal examination was unrevealing. The passage of few drops of blood for a day was considered due to some local lesion, e.g., anal fissure.

Outpatient trials: School children

Four, 5 or 6 logs CFU or placebo were given to a total of 70 children. Vaccinees and household contacts were followed for symptoms and shedding. Once again, no diarrhea, dysentery or severe symptoms were experienced. Loose stools occurred in 15% of vaccinees, but 9% of controls. Abdominal pain was reported in 21% of vaccinees, but 14% of controls. Symptoms were otherwise not more common in vaccinees than in controls, and no dose relationship was apparent. Secondary transmission to household contacts was not demonstrated.

Signs and symptoms in inpatient school children:

Symptoms	4 log (n=3)	5 log (n=3)	6 log (n=3)	Total (n=9)
Diarrhea	0	0	0	0
Loose stool	0	3	1	4
Bloody stool	0	1	0	1
Nausea	1	0	1	2
Vomiting	1	0	0	1
Abdominal pain	1	0	1	2
Fever*	0	0	0	0
Headache	1	0	1	2
Body aches	0	0	0	0
Malaise	1	0	2	3

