Four small trials will be conducted in sequence as part of this protocol. Up to three inpatient trials will be followed by an outpatient trial. The inpatient trials will enroll 18 subjects each, of whom 12 will receive vaccine and 6 placebo. The outpatient trial will enroll 24 subjects, providing vaccine to 16 and placebo to 8. Additionally, as part of assessment for secondary transmission risk, household members will be recruited for participation in a minimal risk aspect of the outpatient trial, collecting only 2 stool samples and symptom responses. No medication or vaccine will be provided to this population, unless symptomatic intestinal disease is apparent and/or the vaccine strain is cultured from their stool. In that case, standard antibiotic treatment will be provided. Assuming 5 household members per vaccinee in the outpatient study, about 100 household members will be enrolled.

As a phase 1 trial in young children, sample size considerations are relatively less important than safety concerns. Our sample size has been determined based on three considerations:

We feel an ethical obligation to perform the trial in as safe a manner as possible. That is why we escalate the dose sequentially in the inpatient studies, providing only the very lowest doses initially, rather than expose all subjects at once. That is also why we expose the fewest number of volunteers possible.

Logistical considerations. How many volunteers are available to participate, and how many can be accommodated and monitored adequately in the facilities at our disposal?

Statistical considerations. With at least 12 volunteers receiving the chosen dose, and

20 placebo, if none of the placebo recipients and a third of the vaccinees experience an adverse event, there will be >80% power to detect this difference with >95% significance level by Fisher Exact Test. Similarly, if none of the placebo recipients sero-convert, and at least one third of the vaccinees at the chosen dose sero-convert, we will be able to detect that difference with >80% power and >95% significance by Fisher Exact Test.

OUTCOME VARIABLES

Clinical

- Adverse events in study subjects.
- Secondary transmission of SC602 to household contacts of vaccinees.
- Adverse events in household contacts of vaccinees.

Laboratory

- Occurrence and duration of fecal shedding of the vaccine strain.
- Immune response as measured by changes in anti-*S. flexneri* 2a LPS secretory IgA in stool, and IgA and IgG in serum.

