Determination of total immunoglobulins: t-IgG, t-IgA concentrations in sera and t-IgG concentrations in fecal extracts will be measured by nephelometry with reagents and a nephelometer (Beckman Instruments Inc. Galway, Ireland).

EIA analyses: All enzyme immunoassay (EIA) results related to antigen-specific responses will be expressed as relative titers, which will be defined as optical density (OD) multiplied by the dilution factor of the sample. The EIA method is described in brief:

EIA plates (Costar Corporation, Cambridge, Mass.) will be coated overnight with antigens in 0.1 M carbonate-bicarbonate buffer (pH 9.6) at 22°C. The plates will be saturated with PBS with 0.05% Tween 20 (PBST) and 1% bovine serum albumin (PBST-BSA). Fivefold dilutions of serum or fecal samples in PBST-BSA will be incubated at 22°C overnight. Enzyme-linked secondary antibodies will be incubated for 4 h at 22°C. Between the various incubation steps, the plates will be rinsed three times with PBST. The enzyme reaction will be developed for 100 min after addition of the substrate p-nitrophenyl phosphate (Sigma), and the OD will be measured at 405 nm. Multiple samples from the volunteers will be always tested in the same plate. The mean OD observed when the sample is replaced with PBST-BSA will define the background level.

Antigen-specific IgG and IgA subclasses of antibodies in serum: In brief, EIA plates will be coated with (i) LPS (10 µg/ml) (in Nunc MaxiSorp plates [A/S Nunc, Roskilde, Denmark]). Serum samples will be applied. As secondary antibodies, biotinylated murine anti-human IgG1 (8c/6-39; Sigma), IgG2(HP-6014); Sigma), IgG3(HP-6050; Sigma), IgG4 (HP-6025; Sigma), IgA1 (A1-18; Sigma), IgA2 (A9604D2; Southern Biotechnology, Birmingham, Ala.), will be used. After incubation and washing, the plates will be incubated with avidin-alkaline phosphates (Sigma) in a 1:4,000 dilution.

Antigen-specific fecal s-IgA antibodies: Diluted fecal samples will be added to the wells of plates coated with the antigen (LPS) (similar to that for serum), and after incubation, a rabbit anti-human secretory component conjugated to horseradish peroxidase (1:3,000 dilution) (Dakopatts, Copenhagen, Denmark) will be used. The enzyme reaction will be developed by adding the substrate (o-phenylene diamine [Dako] in 0.1 M citrate-phosphate buffer containing (0.005% H₂O² pH5.0), and the OD will be measured at 492 nm.

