The data from the vaccine and placebo groups will be compared to determine: a) whether vaccination was associated with increased occurrence of adverse events; b) the extent of secondary spread of the vaccine strain; c) whether there was any vaccine induced outbreak in a bari or neighborhood; and d) the immune response to the vaccine.

The titer of a serum ELISA is the reciprocal of the last dilution with a positive optical density (OD). To show that an individual has responded to the *Shigella* vaccine, a 3-fold increase in titer over the day 0 serum is required for any subsequent sample. In the primary analysis of stool or serum ELISA data, a significant LPS antibody response will be defined as a 3-fold or higher increase in titer after vaccination. In a secondary analysis, the geometric mean titer plus 3 standard deviations of the day 0 samples will be used as a cutoff for significance of antibody response after vaccination.

Use

Combined assessment of shedding, safety and immunogenicity data will serve as the basis for consideration of further investigation of SC602 in expanded safety and efficacy studies of SC602. If personal and community safety, and immunogenicity are demonstrated, then a subsequent protocol will be considered to further evaluate field protective efficacy and safety in larger numbers of children.

MODIFICATIONS TO/DEVIATIONS FROM THE PROTOCOL

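### Every planned analysis of the anti-LPS antibody data is a yes/no cut-off, so none uses the size of the rise; a prespecified log fold-rise comparison beside the responder rate would be a cheap improvement

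*Combined protocol and SAP*

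**What the plan says.** Aim 4 (Specific Aims) and the laboratory list under OUTCOME VARIABLES both describe the immune outcome as changes in antibody: secretory IgA in stool, IgA and IgG in serum. Neither mentions a cut-off.

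DATA MANAGEMENT, 2. Analysis, turns this into responder status. For the individual child, "a 3-fold increase in titer over the day 0 serum is required for any subsequent sample". For the primary analysis of stool or serum data, "a significant LPS antibody response will be defined as a 3-fold or higher increase in titer after vaccination". The secondary analysis is also a threshold: "the geometric mean titer plus 3 standard deviations of the day 0 samples will be used as a cutoff for significance of antibody response".

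That section names no test. SAMPLE SIZE does. Its premise is "With at least 12 volunteers receiving the chosen dose, and" 20 on placebo. It states that "if none of the placebo recipients sero-convert, and at least one third of the vaccinees at the chosen dose sero-convert", the trial can "detect that difference with >80% power and >95% significance by Fisher Exact Test".

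On the scale of measurement, LABORATORY METHODS (EIA analyses) says antigen-specific results are "expressed as relative titers, which will be defined as optical density (OD) multiplied by the dilution factor of the sample", with fivefold dilutions and each child's samples run on one plate. The Analysis section instead takes the serum titer from the furthest dilution that still reads positive.

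**The concern.** Each child contributes a day 0 value and two later values for three antibodies, and the plan keeps one bit of information from each series. A child whose antibody rises 2.5-fold counts the same as a child with no rise. If the vaccine moves most children up by a factor of two or so, most are recorded as non-responders and no other planned analysis would show the shift.

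Immunogenicity is one of the conditions for considering a field efficacy protocol (DATA MANAGEMENT, Use). A real but moderate general rise could therefore be reported as absence of immune response.

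**Working it through.** **Inputs from the plan.** 12 at the chosen dose (a minimum) and 20 on placebo; 1/3 v 0 responders; Fisher's exact test at 5%; 3-fold cut, log10(3) = 0.477. The plan gives no SD of log titer, no expected mean rise and no non-zero placebo rate, so those below are assumptions.

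**Step 1: the plan's own figure.** With 0/20 on placebo, 2/12 gives p = 0.133 and 3/12 gives p = 0.0444, so three responders are needed. Power = P(X ≥ 3), X ~ Bin(12, 1/3) = 1 − (0.0077 + 0.0462 + 0.1272) = 0.819. The stated >80% reproduces. No other test can gain more than 100 − 81.9 = 18.1 points there.

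**Step 2: a general shift.** Assume log10 fold rise is normal with a common SD, mean 0 on placebo. Let q and p be the proportions over 3-fold on placebo and vaccine, and z(q), z(p) the upper-tail normal quantiles. Then SD = 0.477/z(q), mean rise = 0.477 − z(p) × SD, and the standardised difference is z(q) − z(p). Two-sample t power comes from the noncentral t with 30 df and noncentrality [z(q) − z(p)]/√(1/12 + 1/20), where the root is 0.365. Fisher power is by full enumeration.

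| p v q | SD (log10) | Mean rise | Noncentrality | Fisher | Log fold-rise test | Gap |
|---|---|---|---|---|---|---|
| 1/3 v 1% | 0.205 | 2.45-fold | (2.326 − 0.431)/0.365 = 5.19 | 73.4% | 99.9% | 26.5 |
| 1/3 v 2.5% | 0.243 | 2.36-fold | (1.960 − 0.431)/0.365 = 4.19 | 62.3% | 98.2% | 35.9 |
| 20% v 1% | 0.205 | about 2-fold | (2.326 − 0.842)/0.365 = 4.07 | 37.4% | 97.6% | 60.2 |

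**Step 3: larger numbers.** Twelve is a floor. Pooling 6 inpatients at the chosen dose with 16 outpatients gives 22. At 22 v 20 the second row becomes 76.6% v 99.8% (23 points). At 28 v 26 (12 + 16 vaccinees, all placebo) it becomes 82.9% v about 100% (17 points).

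**Step 4: fivefold endpoint titers.** If titer is the last positive dilution, the smallest recordable rise is 5-fold and the 3-fold rule becomes a one-step rule. In simulation with the second row's shift and SD, and an assumed baseline SD of 1.0 on the natural-log scale, Fisher has 59% and a t-test on titer steps 74%, a gap of about 15 points.

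**Step 5: all-or-none response.** Suppose one third respond strongly and two thirds not at all (12 v 20, simulated):

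- 5-fold responders, SD 0.15 log10: Fisher 77%, permutation test on the mean 67%.
- 6-fold, SD 0.17: 76% v 66%.
- 6-fold, SD 0.205: 71% v 61%.
- 4-fold, SD 0.5 natural log (0.5/2.303 = 0.217 log10): Fisher 47.6%, t-test 47.4%.

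So here the cut-off is between level and about 10 points ahead. A rank test does much worse in this pattern (about 35%), which is why the added test should be on the mean.

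**The case against.** **The responder rate is legitimate.** It answers whether an individual child responded, and lack of a cited guideline for 3-fold is not an error. This stands: the responder analysis should stay.

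**All-or-none may be the right picture.** This is a live vaccine, hypothesis 2 links immune stimulation to colonization, and SAMPLE SIZE plans on one third seroconverting. In that pattern the cut-off does as well or better (step 5). This also stands. It makes replacing the primary analysis a debatable trade, but it does not justify having no analysis of size.

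**The titer may not be continuous.** On the Analysis section's definition a 2-fold serum rise cannot be recorded in a child. This stands as a condition: the two definitions need reconciling first. A loss remains on the coarser scale (step 4), under assumed SDs.

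**Small rises are not forecast.** A reader might take "little immune stimulation in this *Shigella*-exposed population" to mean that modest rises are expected here. That sentence summarises the adult trials, and does not say whether adults had small general rises or few responders. The plan's reasoning on age (STUDY SUBJECTS, Age range and gender) is that younger children are more likely to show a significant rise. Modest rises are therefore possible, not predicted.

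**Sample size comes second to safety in this trial.** The plan says so, but the change asks for no more children.

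**Conclusion.** The gap is real: both planned immune analyses are cut-offs, and nothing uses the size of the rise that the aims and outcome list call for. It is a cheap improvement, not a fatal flaw.

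Under a general shift at 12 v 20, the three scenarios computed lose about 27, 36 and 60 points. These rest on log10 SDs of 0.205 to 0.243, small non-zero placebo rates and an equal shift in every vaccinee, none of which is in the documents.

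A reader might infer a single figure for the loss, such as 36 points, or an upper bound. The documents support neither. At the plan's own 1/3 v 0 the ceiling is 18 points, other assumptions give more or less, and an all-or-none response reverses the sign. A reader might also infer that the 3-fold analysis must give up its primary place. That does not follow, because the documents do not settle which response pattern will hold.

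**What to change.** In DATA MANAGEMENT, 2. Analysis:

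1. Keep the 3-fold responder proportion by group, with exact confidence intervals.
2. Prespecify beside it, for serum IgG, serum IgA and stool sIgA, a comparison of chosen dose with placebo in mean log10 fold rise from day 0, using the higher of days 14 and 28. Report a geometric mean fold-rise ratio with 95% CI and a permutation test on the mean.
3. Reconcile the two titer definitions, then use the OD-times-dilution titer from LABORATORY METHODS for this comparison.
4. State before unblinding which comparison is primary.

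The cost is a few sentences, a little programming and one more analysis per antibody, with no new samples or assays. If the fold-rise comparison is made primary and the response proves all-or-none, its power would be somewhat lower than the responder test's, by up to about 10 points in the cases simulated. The responder result would still be reported.
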